#### 8. STATISTICS

#### 8.1 Study Population

All subjects who received at least one dose of study medication with at least one follow up assessment for safety will be included in the safety and tolerability analyses.

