#### **5. STUDY PROCEDURES**

#### 5.1 Cycles:

Cycles will be 28 consecutive days, on a daily or twice a day schedule. Subjects will have an every 6 cycle site visit with +/- 30 days window.

The following observations will be carried out at site study visits every 6 cycles (± 30 days):

- Targeted physical examination,
- Vital signs,
- Overall response assessment (IWG-MRT),
- EORTC QLQ-C30 questionnaire must be completed by the subject consistent with the EORTC guideline or standard guideline for completion of QOL questionnaires (see Appendix section),
- MFSAF questionnaire must be completed by the subject consistent with the standard guideline for completion of QOL questionnaires (see Appendix section)
- Blood draws for:
  - Serum chemistries (see Appendix section)
  - Hematology (CBC with differential and platelets)
- Adverse event assessment,
- Concomitant medication assessment,
- Dispense ruxolitinib, conduct study medication compliance: medication diary review, providing new one in every site visit.

Between study visits, subjects will have hematology (CBC with differential) and serum chemistry on day 1 of every 3 cycles, with +/- 14 days window (see Appendix section).

**Every 3 cycles, in between site visits,** subjects will be contacted for follow-up to assess well-being, any new or worsening signs and/or symptoms, compliance with study medication and dosing instructions, compliance with the local laboratory schedule and to answer any questions that the subject might have.

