#### 5.2 End of Study or Early Termination Visit

End of Study or Early Termination visits are part of the study protocol. However, if the subject has been contacted and cannot/chooses not to return for this visit, this will not be reported as a protocol deviation. This subject decision will be documented on the CRF. Subjects must return any remaining medication to the study site for final drug reconciliation. The following procedures will be performed:

- EORTC QLQ-C30 questionnaire must be completed by the subject consistent with the EORTC guideline or standard guideline for completion of QOL questionnaires (see Appendix section).
- MFSAF questionnaire must be completed by the subject consistent with the standard guideline for completion of QOL questionnaires (see Appendix section).
- Where feasible the EORTC QLQ-C30 and MFSAF questionnaire should be administered prior to any study-specific procedures.
- Review of medical history and concomitant medication,
- Review of any adverse events,
- Complete physical examination and vital signs,
- ECOG performance status,
- Blood draws for:
  - Serum chemistries (see Appendix section)
  - Hematology (CBC with differential),
- Overall response assessment (IWG-MRT),
- A study medication tablet count will be done to assess compliance: medication diary review.

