#### 5.4. Outside Physician Participation During Treatment

MDACC Physician communication with the outside physician is required prior to the patient returning to the local physician. This will be documented in the patient record.

A letter to the local physician outlining the patient's participation in a clinical trial will request local physician agreement to supervise the patient's care (Appendix VI).

Protocol required evaluations outside MDACC will be documented by telephone, fax or e-mail. Fax and/or e-mail will be dated and signed by the MDACC physician, indicating that they have reviewed it.

Changes in drug dose and/or schedule must be discussed with and approved by the MDACC physician investigator, or their representative prior to initiation, and will be documented in the patient record.

A copy of the informed consent, protocol abstract, treatment schema and evaluation during treatment will be provided to the local physician.

Documentation to be provided by the local physician will include drug administration records, progress notes, reports of protocol required laboratory and diagnostic studies and documentation of any hospitalizations.

The home physician will be requested to report to the MDACC physician investigator all life threatening events within 24 hours of documented occurrence.

Patients will return to MDACC every 6 cycles as long as they are enrolled in the study.

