# Serious Adverse Event Reporting (SAE)

An adverse event or suspected adverse reaction is considered "serious" if, in the view of either the investigator or the sponsor, it results in any of the following outcomes:

- Death
- A life-threatening adverse drug experience any adverse experience that places the
  patient, in the view of the initial reporter, at immediate risk of death from the adverse
  experience as it occurred. It does not include an adverse experience that, had it occurred
  in a more severe form, might have caused death.
- Inpatient hospitalization or prolongation of existing hospitalization, unless for planned, elective procedure
- A persistent or significant incapacity or substantial disruption of the ability to conduct normal life functions.
- A congenital anomaly/birth defect.

Important medical events that may not result in death, be life-threatening, or require hospitalization may be considered a serious adverse drug experience when, based upon appropriate medical judgment, they may jeopardize the patient or subject and may require medical or surgical intervention to prevent one of the outcomes listed in this definition. Examples of such medical events include allergic bronchospasm requiring intensive treatment in an emergency room or at home, blood dyscrasias or convulsions that do not result in inpatient hospitalization, or the development of drug dependency or drug abuse (21 CFR 312.32).

- Important medical events as defined above, may also be considered serious adverse events. Any important medical event can and should be reported as an SAE if deemed appropriate by the Principal Investigator or the IND Sponsor, IND Office.
- All events occurring during the conduct of a protocol and meeting the definition of a SAE must be reported to the IRB in accordance with the timeframes and procedures outlined in "The University of Texas M. D. Anderson Cancer Center Institutional Review Board Policy for Investigators on Reporting Unanticipated Adverse Events for Drugs and Devices". Unless stated otherwise in the protocol, all SAEs, expected or unexpected, must be reported to the IND Office, regardless of attribution (within 5 working days of knowledge of the event).
- All life-threatening or fatal events, that are unexpected, and related to the study drug, must have a written report submitted within 24 hours (next working day) of knowledge of the event to the Safety Project Manager in the IND Office.

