- Unless otherwise noted, the electronic SAE application (eSAE) will be utilized for safety reporting to the IND Office and MDACC IRB.
- Serious adverse events will be captured from the time of the first protocol-specific intervention, until 30 days after the last dose of drug, unless the participant withdraws consent. Serious adverse events must be followed until clinical recovery is complete and laboratory tests have returned to baseline, progression of the event has stabilized, or there has been acceptable resolution of the event.
- Additionally, any serious adverse events that occur after the 30 day time period that are related to the study treatment must be reported to the IND Office. This may include the development of a secondary malignancy.

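### Section 8.1 makes the only safety set depend on an undefined post-dose assessment; read narrowly, it omits treated subjects who leave early without a termination visit

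*Combined protocol and SAP*

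**What the plan says.** Section 8.1 gives the single analysis population in Section 8, used for safety and tolerability: "All subjects who received at least one dose of study medication with at least one follow up assessment for safety will be included". Section 8.3 then tabulates adverse event incidence. No section states which contacts, tests or reports meet the second condition.

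These sections bear on what might count:

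- **Section 5.1, scheduled assessments.** Between site visits there is hematology and "serum chemistry on day 1 of every 3 cycles, with +/- 14 days window". Also every 3 cycles, "subjects will be contacted for follow-up to assess well-being, any new or worsening signs and/or symptoms". Site visits come every 6 cycles and list an adverse event assessment.
- **Section 5.2, termination visit.** It includes a review of adverse events, but "if the subject has been contacted and cannot/chooses not to return for this visit, this will not be reported as a protocol deviation".
- **Section 5.4, local care.** "Documentation to be provided by the local physician will include drug administration records, progress notes", together with laboratory reports and records of hospitalization.
- **Section 7, serious events.** "Serious adverse events will be captured from the time of the first protocol-specific intervention, until 30 days after the last dose of drug". Unless the protocol says otherwise, "all SAEs, expected or unexpected, must be reported to the IND Office, regardless of attribution". In addition, "Serious adverse events must be followed until clinical recovery is complete and laboratory tests have returned to baseline".
- **Section 5.5, exits.** Death and loss to follow-up are both listed as reasons for removal.

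**The concern.** A safety set normally rests on exposure alone. Here a subject must also have something recorded after the first dose, and the reader is not told what. If that something is a scheduled contact, entry to the tables depends on staying in the study long enough to reach it. The subjects most likely to fail that condition include those who die or stop early because of an adverse event.

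Section 1 makes long-term safety and tolerability the main objective, and the Section 8.3 incidence tables are how adverse events are reported. Two things are at stake. An early fatal or serious event could be captured under Section 7 and still be missing from those tables. Two analysts could also build different denominators from the same data, each consistent with the text.

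**Working it through.** The plan states no sample size, event rate or exit rate, so there is no figure to reproduce. The steps below use the protocol's schedule where they can and mark every other input as assumed.

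**1. When the first scheduled assessment falls** (28-day cycles, Section 5.1). The 3-cycle laboratory test can be read in two ways:

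- Day 1 of cycle 3: 2 × 28 + 1 = day 57; with ±14 days, day 43 to 71.
- Day 1 after three full cycles: 3 × 28 + 1 = day 85; with ±14 days, day 71 to 99.

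The contact has no stated window. If only site visits counted, the gap would be about 6 × 28 = 168 days.

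**2. Who is in the set under each reading**

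| Treated subject who, before that point, … | Scheduled assessments only | Any post-dose safety information |
|---|---|---|
| stops and attends the termination visit | in | in |
| dies, with the event captured under Section 7 | out | in |
| stops, is contacted, declines the visit | out | in, if the contact counts |
| is lost, but local records exist | out | in |
| is lost, with no information | out | out |

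The readings differ in the three middle rows. No section chooses between them.

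**3. How many subjects could be affected (assumed).** The share leaving before day d at a constant annual exit rate a is 1 − (1 − a)^((d − 1)/365.25).

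| a | before day 57 | before day 85 |
|---|---|---|
| 5% | 0.78% | 1.17% |
| 10% | 1.60% | 2.39% |
| 20% | 3.36% | 5.00% |

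From the smallest to the largest of these shares, the expected number is 0.16 to 1.00 subjects at N = 20, 0.31 to 2.00 at N = 40, and 0.47 to 3.00 at N = 60. These are all exits. Anyone who attends a termination visit stays in the set, so the number excluded is lower.

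**4. Effect on a reported incidence (assumed).** Let E of N treated subjects have the event, and let k be excluded, of whom e had it. The reported rate is (E − e)/(N − k). It is below E/N only if e/k exceeds E/N. With N = 40 and E = 8:

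- none excluded: 8/40 = 20.0%;
- one excluded who had the event: 7/39 = 17.9%;
- one excluded who did not: 8/39 = 20.5%.

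So the direction is not fixed. If the event is death, at a constant rate over an assumed T years, the expected number before day 85 is 40 × (1 − 0.8^(84/(365.25 T))). This gives 1.0 for T = 2, 0.7 for T = 3 and 0.4 for T = 5. One excluded death is therefore a reasonable illustration for a long-term study.

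**5. Effect of an all-treated set (assumed).** Suppose 38 subjects have data, 20 of them with a given adverse event, and 2 more have no post-dose information. The current rule gives 20/38 = 52.6%. All treated gives 20/40 = 50.0%. If both uninformative subjects had the event, the rate would be 22/40 = 55.0%.

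**The case against.** The strongest reply is that the narrow reading adds a word. Section 8.1 does not say the assessment must be scheduled, and the protocol plainly expects safety information from elsewhere: serious event capture from the first intervention, local-physician records, adverse event entry into the study database, and platelet counts that Section 4.4 presupposes between the 3-cycle tests. On that reading the excluded subjects have no information, so no known event is lost. This largely stands, and it is why the point is an ambiguity. A reader might infer that early deaths will be left out of the tables; the documents do not establish that. They do not rule it out either. Section 5.1 attaches the idea of follow-up to the 3-cycle contact, and no text says that a death or serious event report places a subject in the set.

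Second, a subject who stops early and attends the termination visit has had an adverse event review and is in the set on either reading. That stands and limits the point.

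Third, Section 8 plans no death rate as such, so a death enters these tables only through a fatal adverse event. That also stands.

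Fourth, an all-treated set counts subjects without information as event-free and can make the drug look slightly safer. The effect is real, but showing how many such subjects there are lets a reader bound it. A one-line definition of the qualifying assessment would also remove the ambiguity. It would still leave entry to the set depending on what happens after dosing.

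**Conclusion.** The point holds as a minor one. The only safety set has an undefined entry condition that depends on a post-treatment event, and on one permissible reading some early exits leave the adverse event tables.

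The size is probably small: Section 3.1 admits only subjects already benefiting from the drug, and a termination visit keeps many early leavers in. It cannot be computed, since neither N nor the number excluded is given. The exit rates (5% to 20% a year), sample sizes (20 to 60) and event counts used above are all assumptions.

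Two stronger inferences fail. The rule does not weaken safety reporting: Section 7 sends serious events to the IND Office and adverse events into the database regardless of Section 8.1, and Section 7.1 puts myelosuppression and its complications in the study summary with no population restriction (though that does not cover all deaths or serious events). Nor does the rule bias rates in one known direction, as step 4 shows. Section 8.2 plans summary statistics only, so no test or decision rule is affected.

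**What to change.** In Section 8.1, replace the sentence with three:

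- the safety and tolerability set is every subject who took any study drug under this protocol;
- every adverse event, serious adverse event and death reported for these subjects is counted, whether or not a scheduled assessment took place;
- the number of subjects with no post-dose safety information is shown beside the adverse event tables.

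In Section 8.4, add one sentence that limits only the change-from-baseline and shift summaries to subjects with a post-baseline value.

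The cost is four sentences and no new data collection. The laboratory and vital-sign change and shift summaries will carry their own denominators. Subjects without information enter the adverse event denominator as event-free, which can lower some rates slightly (52.6% to 50.0% in the assumed example). The displayed count lets a reader set the bounds (50.0% to 55.0% there).

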# 8.2 Safety Analysis

The clinical safety data (vital signs, routine laboratory tests and adverse events) will be analyzed using summary statistics (e.g., mean, frequency).

#### **8.3 Adverse Events**

Severity of adverse events will be based on the NCI–CTCAE v3.0 (NCI Common Terminology Criteria for Adverse Events, Publ. Aug 9, 2006). The subset of adverse events that are considered by the Investigator to have a possible or probable relationship to study medication will be considered to be treatment-related adverse events. If the Investigator does not specify the relationship of the adverse event to study medication, the adverse event will be considered to be treatment-related. The incidence of adverse events and treatment-related adverse events will be tabulated.

#### 8.4 Clinical Laboratory Tests and Vital Signs

Laboratory test values outside the normal range will be assessed for drug association based on screening and baseline values and for severity based on the normal ranges for the clinical reference laboratory. The incidence of abnormal laboratory values and shift tables relative to baseline will be tabulated.

Descriptive statistics and mean change from baseline will be determined for vital signs (blood pressure, heart rate, respiratory rate and body temperature) at each assessment time. Vital sign results will be reviewed for clinically notable abnormalities and patients exhibiting clinically notable vital sign abnormalities that were not present at screening or baseline will be listed.

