#### 2.3 Ruxolitinib Potential Risks

The primary clinical risks with ruxolitinib treatment are the potential sequelae of decreased hematopoiesis, myelopoiesis, thrombopoiesis and decreased levels of circulating cytokines and growth factors, all of which are secondary to the inhibition of growth factor pathways by JAK2 antagonism.

The most frequently reported hematologic adverse reactions (any CTCAE Grade) are anemia, thrombocytopenia, and neutropenia. Increased rates of infection and anemia are potential risks of myelosuppression. Anemia can also lead to increase in number of transfusions. Hematologic parameters will be closely monitored for all subjects during this study, and therapy will be withdrawn or dosing held or reduced until resolution if there are clinically relevant declines.

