#### 3. PATIENT ELIGIBILITY

#### 3.1 Inclusion Criteria:

 Currently enrolled in study 2007-0169 and benefiting from therapy as determined by treating physician,

- Eastern Cooperative Oncology Group (ECOG) performance status of 0, 1, or 2 at enrollment of this study,
- Ability and agreement to attend protocol-specified visits at the study site,
- Able to comprehend and willing to sign the informed consent form.
- Negative pregnancy test in females of childbearing potential. Male patients with female partners of child-bearing potential and female patients of childbearing potential are required to use two forms of acceptable contraception, including one barrier method, during their participation in the study and for 30 days following last dose. Acceptable forms of contraception include 1 highly effective method such as an intrauterine device (IUD), hormonal (birth control pills, injections, or implants), tubal ligation, or partner's vasectomy and at least 1 additional approved barrier method such as a latex condom, diaphragm, or cervical cap. Female patients of childbearing potential must not be breast-feeding or planning to breast feed and must have a negative pregnancy test ≤7 days before first study treatment.

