## 4.4 Dosing Delays/Dose Modifications/Dose Interruptions

The course of management of the subject is at discretion of the investigator as determined in the best interest of the subject. For subjects who do not require dose interruption but have thrombocytopenia or neutropenia and no other serious safety concerns, strategy may vary case-by-case situation, to include one or more aspects of dosing schedule (ex. daily dose regimen, dosing interval, and frequency of dose or overall duration of administration of the therapy) as well as concomitant treatments to manage any untoward symptoms.

Mandatory dose decreases for safety reasons are dictated by platelet count levels. Dose modification strategies will be applied to all ongoing subjects enrolled in the study as per ruxolitinib's label (guidelines provided by FDA). When a decision is made to discontinue the subject or interrupt the therapy, then the recommendation is to consider instituting a tapering strategy based on the investigator's clinical judgment.

Utilization of a tapering strategy is based on condition of the subject, the current dosing regimen and the investigator's clinical judgment, and maintains a dose that has been shown to provide benefit to the subject or to increase the dose to a dose previously shown to provide benefit to the subject.

In any case, the following rules will ALWAYS apply:

- 1. The maximum dose must never exceed 25 mg BID, or if once-daily doses are used, dose may never exceed 100 mg QD.
- 2. Dosing must be interrupted with observation of a platelet count <25 x  $10^9$ /L.Dosing may be resumed with recovery of platelet count to a confirmed value of 35 x  $10^9$ /L or higher. Doses should be restarted at 5 mg BID, and may be increased by 5 mg BID every 2 weeks provided platelet count remains stable and exceeds 35 x  $10^9$ /L.
- 3. Dosing should be decreased by at least 5 mg BID increments with confirmed platelet count values of 25 x  $10^9/L$  to 35 x  $10^9/L$ . Dose increases may be instituted with recovery of platelets above  $50 \times 10^9/L$ .

Drug may be held up to 2 months for platelet or ANC abnormalities but if counts do not return to the level for reinstituting drug by that time, the subject will be discontinued from the study. Similarly, if drug is held for a non-hematologic toxicity for greater than two months, then the subject must be discontinued from the study.

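### Section 8.4 ties laboratory severity to the normal range and leaves the shift categories undefined, so falls to the protocol's own platelet action levels may not show in the shift tables

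*Combined protocol and SAP*

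**What the plan says.** Section 8.4 is the only part of the plan specific to laboratory values. Out-of-range values are to be assessed "for severity based on the normal ranges for the clinical reference laboratory". The output is then described in one sentence: "The incidence of abnormal laboratory values and shift tables relative to baseline will be tabulated". The section does not say what the categories of the shift table are. It mentions neither CTCAE grade, nor a platelet threshold, nor a worst on-study value.

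Elsewhere the protocol treats depth of cytopenia as central:

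- Section 2.3: "The most frequently reported hematologic adverse reactions (any CTCAE Grade) are anemia, thrombocytopenia, and neutropenia".
- Section 4.4: "Mandatory dose decreases for safety reasons are dictated by platelet count levels". It sets action levels at 25, 35 and 50 x 10^9/L; for the lowest, "Dosing must be interrupted with observation of a platelet count <25" x 10^9/L.
- Section 3.1 admits patients "Currently enrolled in study 2007-0169 and benefiting from therapy as determined by treating physician". Neither 3.1 nor 3.2 sets a limit on platelets, hemoglobin or neutrophils.

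Three other places bear on how low counts would be reported. Section 8.2 applies summary statistics, with means and frequencies as examples, to routine laboratory tests. Section 8.3 grades adverse events by CTCAE and tabulates their incidence. Section 7.1 sends myelosuppression and its complications to the study summary.

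**The concern.** A normal range says whether a value is low, not how low. Platelet counts of 140 and 20 x 10^9/L are both low if the lower limit is 150, and all three action levels of Section 4.4 sit in that one category. A subject who enters below range and later reaches the interruption level need not change category at all. The same logic applies to hemoglobin and neutrophils.

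The main objective (Section 1) is long-term safety and tolerability, every subject is already taking the drug at entry, and the drug's primary risks are hematologic. If the shift tables cannot separate mild from severe cytopenia, they say least about the toxicity that matters most.

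**Working it through.** The plan states no rate, sample size or power for this analysis, so there is no figure to reproduce. Two questions were checked: what a low/normal/high table does with a given fall, and how often that would matter.

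**1. Individual falls.** The documents give no lower limit of normal (LLN) for platelets; 130, 140 and 150 x 10^9/L were assumed. Each baseline below falls to 20 x 10^9/L.

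| Baseline | Low/normal/high | Bands cut at 25, 35, 50, 100 |
|---|---|---|
| 40 | low-to-low at every LLN | down 2 bands |
| 60, 90 | low-to-low at every LLN | down 3 bands |
| 120 | low-to-low at every LLN | down 4 bands |
| 145 | low-to-low at LLN 150; normal-to-low at 130 or 140 | down 4 bands |
| 180, 250 | normal-to-low at every LLN | down 4 bands |

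The band limits 25, 35 and 50 come from Section 4.4, and 100 from the remission criteria in Section 6. With bands, no tested fall is hidden. With low/normal/high, a fall from 180 to 20 is visible but looks the same as a fall from 180 to 125.

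**2. Share hidden, simple formula.** Let p be the share of subjects below LLN at baseline, and RR the risk of falling below 25 in those subjects relative to the rest. The share of such falls that is low-to-low is p x RR / (p x RR + 1 - p).

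- p = 10%, RR = 1: 0.10 / (0.10 + 0.90) = 10%.
- p = 25%, RR = 5: 1.25 / (1.25 + 0.75) = 63%.
- p = 50%, RR = 3: 1.50 / (1.50 + 0.50) = 75%.
- p = 90%, RR = 5: 4.50 / (4.50 + 0.10) = 98%.

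The formula alone spans 10% to 98%. An RR of 1 is hard to defend, because a subject at 60 needs a much smaller fall to reach 20 than a subject at 250.

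**3. Share hidden, assumed distributions.** Baseline platelets are lognormal with log-SD 0.6, and LLN is 150. The share starting low is Phi(ln(150/median)/0.6); for a median of 100, Phi(0.405/0.6) = 75%. The worst on-study count is baseline x exp(-|D|), with D normal. Three choices of mean and SD for D were used: A (0.35, 0.45), B (0.7, 0.6) and C (0.35, 0.8). A new fall below 50 means baseline at or above 50 and worst count below 50; likewise for 25. Cells give the simulated percentage of new falls that are low-to-low, below 50 / below 25.

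| Median | Start low | A | B | C |
|---|---|---|---|---|
| 100 | 75% | 98 / about 100 | 92 / 98 | 92 / 98 |
| 160 | 46% | 95 / about 100 | 81 / 94 | 80 / 91 |
| 200 | 32% | 93 / over 99 | 73 / 90 | 71 / 85 |
| 250 | 20% | 89 / 99 | 63 / 85 | 61 / 76 |

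The range is about 60% to 98% for new falls below 50, and 76% to about 100% below 25. The decline model matters as much as the baseline median. Lowering the LLN to 130 in the same model takes the smallest values to about 49% and 66%.

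**The case against.** The strongest reply is that Section 8.4 does not say low/normal/high. It promises shift tables and leaves their categories open, and assessing the severity of values already out of range could imply some gradation among them. A table by grade would be compatible with the text. That stands: the low-to-low result is conditional. But the normal range is the only scale the section names, so a programmer working from it would most naturally use low, normal and high. If something else is meant, the section needs to say so.

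A reader might also infer that most of this cohort enters with low counts. The documents do not show it. Section 2 describes progressive anemia in the disease and Section 2.3 lists the cytopenias as frequent reactions, but neither gives a proportion and no baseline distribution appears anywhere. The point does not need it: with only 20% starting low, most new falls to these levels were still low-to-low at an LLN of 150.

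A third reply is that severe cytopenia could surface elsewhere: as a CTCAE-graded adverse event (Section 8.3), in the summary statistics (Section 8.2), or in the study summary (Section 7.1). That is fair, so the plan cannot be said to omit severe cytopenia. But Section 8.3 promises incidence and does not state tabulation by grade, a mean hides individual low points, and Section 7.1 gives no format. None guarantees a count of subjects below 25 x 10^9/L.

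Finally, the percentages rest wholly on assumptions. That is true, and they should be read as an illustration.

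**Conclusion.** The point holds in conditional form. Section 8.4 uses a severity scale that cannot distinguish mild from severe cytopenia, does not link it to the platelet levels of Section 4.4, and leaves the shift categories undefined. If low/normal/high is used, falls to those levels in subjects already below range will not register as shifts, and falls from the normal range will register without their depth.

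How many events this affects cannot be known from the documents. Under the assumptions above (baseline median 100 to 250, log-SD 0.6, LLN 150, three decline models) it is about 60% to 98% of new falls below 50 and 76% to about 100% of new falls below 25 x 10^9/L. The documents do not support the stronger readings that the cohort is mostly cytopenic at entry, that these falls will certainly be tabulated as no shift, or that severe cytopenia will be absent from the report. In a descriptive study with safety as its main objective, this should be corrected before the tables are programmed.

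**What to change.** In Section 8.4:

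- For tests that CTCAE grades, tabulate baseline grade by worst on-study grade, using all available counts (site, local and unscheduled), and state which count is the baseline for these roll-over subjects.
- Use one CTCAE version. Section 7 names 4.0 and Section 8.3 names 3.0; the two must be reconciled first.
- Report the number of subjects whose lowest on-study platelet count was below 50, 35 and 25 x 10^9/L.
- Keep normal-range tables for tests without a CTCAE grade.

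The cost is a few sentences and slightly more table programming. Section 5.1 already schedules blood counts at site visits every 6 cycles and between visits every 3 cycles, so no new data are needed. This is a reporting change only and implies no view on the dosing thresholds.
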